6.05) Justification:	Because the proposed study examines the effect of maternal interpretation biases on child interpretation biases and child anxiety symptoms in children aged 8-12, such school-aged children will be included in the proposed study. This age range was specifically chosen as children age 7 and younger may lack critical cognitive skills that are central to the experience of anxiety (e.g., mental rehearsal of anticipated negative outcomes and/or consequences; Borkovec, 1994). Also, children under the age of 8 may show poor reliability on self-report measures. Given that peer influence dramatically increases in adolescence (Steinberg, 2005), an upper limit of 12 years was chosen in order to minimize the role of peers in child interpretation biases and maximize our ability to isolate the effects of parental interpretation biases on outcomes of interest. We are also excluding children with IQ scores < 80 and reading comprehension composite < 75 given the cognitive and reading demands presented by the computerized tasks. Likewise, children with a physical disability preventing them from using a computer are excluded. This study also focuses on mothers as 69-75% of caregivers are women, and female caregivers spend as much as 50% more time providing care to children than male caregivers (U.S. Census Bureau, 2012). A second consideration involved whether to include mothers receiving treatment for anxiety (psychosocial [e.g., CBT] or pharmacological). Due to the emphasis of CBT on thoughts (e.g., interpretation biases) and the effects of anxiolytics on anxious behavior, we chose to exclude mothers involved in psychosocial treatment for anxiety and/or mothers who underwent changes in pharmacological treatment during the 12 weeks prior to enrollment.
6.06) Determination:	Mothers who contact project staff will be provided with information about the study and screened for inclusion/exclusion criteria. Mothers who appear eligible will be invited for the first session. Upon arrival, consent (and assent) will be obtained. Consenting families will undergo an in person comprehensive psychosocial assessment including structured clinical interviews, child and parent questionnaires, and an abbreviated IQ and

	reading test.
7) If this study proposes to include children, this inclusion must meet one of the following criterion for risk/benefits assessment according to the federal regulations (45 CFR 46, subpart D). Check the appropriate box:	(404) Minimal Risk

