11) Describe the research study design. (Describe the research methods to be employed and the variables to be studied. Include a description of the data collection techniques and/or the statistical methods to be employed.)	
The study involves two sessions on separate days. All sessions take place at the University of Houston. All parent-child dyads will complete multi-method assessments of interpretation biases and anxiety disorder symptoms (and other forms of psychopathology). Clinically anxious mothers of children with anxiety disorders will be randomly assigned to either a computerized training paradigm that teaches them to interpret child-related ambiguous situations in a positive manner (n=65; "positive training" condition) or a neutral condition that does not train interpretation of such situations in either a positive or negative direction (n=65; "neutral" condition). Specifically, in the "positive training" condition, a child-related scenario will be presented on the computer screen (e.g. meet the teacher day). Two possible interpretations of the event are subsequently presented on the screen: a threatening and a non-threatening interpretation. Mothers will be asked to choose the most accurate interpretation of the event by pressing on the corresponding key on the keypad. Mothers will receive positive feedback and a brief explanation when they choose the positive interpretation explanation, and negative feedback and a brief explanation when they choose the negative interpretation explanation. Mothers randomly assigned to the neutral condition will not receive any feedback on their answers. Children will subsequently be asked to participate in an anxiety-provoking speech task. Prior to this task, they will have the opportunity to discuss how they will approach the task with their mother, and their mothers' behavior during this interaction will be coded. Following the discussion, children and mothers will be asked how threatening they perceive the task to be and will complete a second computerized assessment of interpretation biases to assess interpretation biases post-training. Finally, children's anxiety, heart rate, and performance on the task will be assessed.

	This study involves two sessions on separate days. During the first session, mothers and children will complete several paper and pencil questionnaires (attached) that ask questions about the child's thoughts, feelings, and

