
12) Describe each task subjects will be asked to perform.
	
behaviors. Mothers will also be interviewed about their child's mood and behavior using the the MINI International Neuropsychiatric Interview. Children will also complete a brief assessment of intellectual and reading ability using a short form of the WISC-IV (Vocabulary and Block Design) and two subtests of the WIAT-III (Reading Comprehension and Oral Reading Fluency), respectively. This session is expected to last approximately 2 hours. During the second visit (within two weeks of the first visit), mothers and children will complete a computer task (described in detail in attached document labeled "Measures") that will ask about relationships between words and sentences. Second, mothers will be randomly assigned to one of two groups. The first group will complete a computer task that will ask about relationships between words and sentences while receiving feedback about their responses. The second group will complete a computer task that will ask about relationships between words and sentences but will not receive feedback about their responses. After completing this task, mothers will be asked to complete the first computer task again. Third, mothers will be asked to talk with their child about how he/she will give a brief speech describing his/her family in front of a recording video camera. The child's heart rate will be monitored during the speech. This involves placing one sensor (electrode) on the child's right-side collarbone, one sensor on the child's left-side collarbone, and one sensor on the left side of your child's rib cage. This second session is expected to last approximately 1 hour.

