
13) Describe how potential subjects will be identified and recruited? (Attach a script or outline of all information that will be provided to potential subjects. Include a copy of all written solicitation, recruitment ad, and/or outline for oral presentation.)
	
Recruitment strategies will include the use of a multi-media advertising campaign targeting: (1) the Sleep and Anxiety Center of Houston (SACH); (2) mental health provider offices within the local community; (3) outpatient clinics throughout the Houston, TX metropolitan area; (4) community pediatric primary care clinics; (5) public/private schools and summer camps; (6) churches, community organizations and centers; (7) local colleges and universities; (8) coffee shops, bookstores, and grocery stores; and (9) direct outreach at local health fairs. Regarding number (1) above, information about the study (i.e., the study's flyer) will be posted on the SACH website, including contact information. Study flyers will also be posted in the waiting area for SACH and made visible to patients. Patients who ask SACH personnel about the study will be told to contact the number listed on the study's flyer. We will also do direct mailings of study information to households of children enrolled in surrounding school districts. Flyers/ advertisements will specifically recruit mothers and children with a range of clinical anxiety symptoms by specifying that we are looking for children and parents who are stressed, anxious, worried, nervous, or shy. Children who meet diagnostic criteria for a psychiatric disorder will be referred for appropriate treatment services.

	
Recruitment materials will instruct interested individuals to call the laboratory for further information about the study. The mothers or female guardians of all prospective participants will be screened by phone (according to the inclusion and exclusion criteria described above), and informed about the basic study procedures. Those whose children appear to meet criteria for the study and who express an interest in participating will be invited to schedule a visit for the first session. Upon arrival, the nature and purpose of data collection will be explained to parents by a member of the research team.

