
14) Describe the process for obtaining informed consent and/or assent. How will investigators ensure that each subjects participation will be voluntary (i.e., free of direct or implied coercion)?
	
During this visit, mothers and children will also be asked to provide written informed consent and assent, respectively. In particular, mothers and their children will be informed that the purpose of this study is to examine how maternal personality characteristics influence children’s behaviors and feelings. Mothers and children will be informed that the study will involve completing two assessment visits, and that both visits will take place in the PI’s laboratory at University of Houston. Children (in the presence of their caregiver) and mothers will be informed that they will be asked to complete self-report questionnaires and interviews pertaining to the parent and the child’s personality, behaviors, mood, and emotions. Mothers and children will also be informed that the assessment sessions will additionally involve having the mother and child complete computerized assessments of interpretation biases (one before the mother completes the interpretation bias training program, and one after), and the mother will be informed of her participation in the computerized training program. Finally, children will be informed that they will be asked to engage in a speech task, during which their heart rate will be monitored continuously. The procedures for collecting heart rate will be described in detail, including the need to adhere sticky sensors on the child’s anterior left and right shoulders, and on the left rib cage below the pectoral muscle. Mothers and children will be informed that it is quite normal for electrodes to leave a slight ring on the skin for a few hours. In addition to being informed about the study procedures, mothers and children will be informed of the potential risks of participating, including that they may experience boredom, distress, discomfort, anxiety, frustration, or fatigue as a result of completing the questionnaires, interviews, computer and speech tasks. They will also be informed that they may withdraw their consent to participate at any time without negative consequences. Finally, participants will be informed verbally and in writing about the steps that will be taken to protect their confidentiality, as well as the limits of confidentiality. In particular, participants will be informed that any reports of child abuse or neglect (as well as abuse of the elderly) will be reported, as will the report of active suicidal or homicidal intent. Participants (both children and their parents/guardians) will have the opportunity to direct questions to the experimenter (as well as Drs. [name] or [name]) to clarify any information provided in the informed consent document. Following the provision of written informed assent and consent, the child and her/his parent/guardian will be taken to separate rooms to complete their respective assessment measures (thereby ensuring the child’s privacy as well as the confidentiality of her/his responses). At the end of the study, all participants will be given contact information for the laboratory.

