Analyses 2.1: Related to H2 and H3, Holm's (1979) modified Bonferroni-corrected independent-samples t-tests will examine mean group differences (positive training vs. neutral training) in child and maternal ratings of perceived threat prior to the anxiety-provoking speech task.

Analyses 3.1: Related to H4.1, coding of child anxious behavior will be first subjected to similar procedures described for H1 above. A two-group (positive training vs. neutral training) one-way MANOVA (4 DVs: facial expression, body movements, speech quality, and content) will be used to examine the effects of the positive interpretation bias training paradigm on child behavior during the parent-child discussion. If the MANOVA is significant, the follow-up procedures will be identical to those reported above (see Analyses 1.1.). To address H4.2, ANCOVAs (controlling for baseline RSA) will be used to examine between group (positive training vs. neutral training) mean differences in children's RSA. Finally, we will conduct independent-samples t-tests to examine mean group differences in overall observer-rated performance during the speech (H4.3).

Analyses 4.1: Related to H5, a hierarchical linear regression will be conducted using child anxiety during the speech task as dependent variable in order to examine child SoP diagnosis as a moderator of associations between maternal interpretation biases child anxiety symptoms. Predictor variables will be mean-centered. In the first step of the model, any necessary control variables will be entered. In the second step, both maternal interpretation biases and child SoP diagnosis will enter the model as predictor variables. In the third step, a maternal interpretation biases X child SoP interaction term will enter the model as a predictor.

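### The speech task is disclosed up to two weeks before the mother is trained, and Analyses 2.1 use no pre-training threat rating: a possible loss of sensitivity, not a bias

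*Combined protocol and SAP*

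**What the plan says.** - **Timing of consent.** Item 6.06 places it at the first session: "Upon arrival, consent (and assent) will be obtained".
- **What the child is told.** Item 14: "Finally, children will be informed that they will be asked to engage in a speech task".
- **What the mother is told.** Item 14's risk statement is addressed to mothers and children together and covers distress or anxiety "as a result of completing the questionnaires, interviews, computer and speech tasks". She therefore knows of the speech from session 1. At the phone screen she is also "informed about the basic study procedures" (item 13); whether that includes the speech is not stated.
- **The gap.** Item 12: "During the second visit (within two weeks of the first visit), mothers and children will complete a computer task". Item 11 says the sessions are on separate days. No minimum gap is given.
- **Session 2 order (item 12).** Mother and child do a computer task; the mother is then randomised and trained; then mother and child discuss the speech.
- **Role of the discussion (item 11).** "Prior to this task, they will have the opportunity to discuss how they will approach the task with their mother".
- **Threat rating (item 11).** "Following the discussion, children and mothers will be asked how threatening they perceive the task to be". No earlier threat rating is described.
- **Analysis.** Analyses 2.1 use Holm-corrected independent-samples t-tests of "mean group differences (positive training vs. neutral training) in child and maternal ratings of perceived threat prior to the anxiety-provoking speech task". Among the Aim 3 outcomes, only RSA has a stated baseline covariate.

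**The concern.** The design intends a chain: training changes the mother, the changed mother talks to the child, and the child's view of the speech shifts. The manipulated part of that chain is one discussion in a session of about an hour. Before it, a clinically anxious, still untrained mother and a child with an anxiety disorder who lives with her have up to two weeks in which both know a speech is coming. The protocol's own reason for the lower age limit is that children in this range can mentally rehearse feared outcomes (item 6.05).

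If some dyads do talk the speech through at home, two things could follow. Some children may be harder to move by the time of the planned discussion, which would shrink the arm difference. Dyads may also differ more in where they start, partly because the gap varies, which would add variance to the child's threat rating and to the speech outcomes. A rating taken only after the discussion cannot separate starting position from response, and an unadjusted t-test leaves that variation in the error term.

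**Working it through.** **1. Sequence.** Items 6.06, 11, 12 and 14, read together, give: disclosure to both (session 1), a gap of up to two weeks, pre-training computer task, randomisation, training, discussion, threat rating, speech. The order is consistent across these items. No visible item asks dyads not to discuss the speech, asks whether they did, or takes a threat rating before training.

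**2. Bias.** Disclosure comes before randomisation and is the same for every dyad. Any home discussion is therefore balanced between arms in expectation, and the mean difference is not biased towards a false positive.

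**3. Which hypotheses are exposed.** Hypothesis 2.2 (child's threat rating) and 3.1 (speech outcomes) need the effect to pass from mother to child. Hypothesis 2.1 (mother's own rating) does not; training acts on her directly.

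**4. Size.** The documents give no alpha, power, effect size, SD or correlation, so there is no stated power to reproduce. The only check is 65 + 65 = 130, which agrees with the stated total. The rest is illustration. Only the 65 per arm and the use of Holm come from the documents.

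Assumptions: two-sided alpha 0.05, or 0.05/2 = 0.025 at the first Holm step over the two ratings; d = 0.5; correlation r of 0.5 to 0.7 between a pre-randomisation rating and the later one.

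*Unadjusted t-test.* Non-centrality = d × √(n/2) = 0.5 × √32.5 = 2.850, with 128 df.
- Critical t 1.979 (alpha 0.05): power 0.808.
- Critical t 2.268 (alpha 0.025): power 0.719.

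*ANCOVA.* Residual variance is multiplied by 1 − r², a cut of 25% at r = 0.5 and 49% at r = 0.7. Non-centrality = d × √(n/2) / √(1 − r²), with 127 df.
- r = 0.5: 2.850/0.866 = 3.291
- r = 0.7: 2.850/0.714 = 3.991

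| Analysis (d = 0.5) | alpha 0.05 | alpha 0.025 |
|---|---|---|
| t-test | 0.808 | 0.719 |
| ANCOVA, r = 0.5 | 0.904 | 0.846 |
| ANCOVA, r = 0.7 | 0.977 | 0.956 |

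**5. What dilution would do, if it occurred.** Suppose the effect shrank by 20%, to 0.8 × 0.5 = 0.40. The 20% is arbitrary.

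| Analysis (d = 0.40) | alpha 0.05 | alpha 0.025 |
|---|---|---|
| t-test | 0.62 | 0.51 |
| ANCOVA, r = 0.5 | 0.74 | 0.64 |
| ANCOVA, r = 0.7 | 0.89 | 0.82 |

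The effect being estimated stays at 0.40 in every row. At alpha 0.05, the 0.89 exceeds the 0.81 of an undiluted t-test, which shows that the covariate gain is ordinary baseline adjustment and not repair of the dilution.

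**The case against.** The strongest reply is that dilution is conjecture. Nothing in the documents says dyads discuss the speech at home, or that such talk fixes a child's appraisal. If it only shifts where children start, the mean difference is unchanged, and higher initial threat might even leave more room for training to work. Maternal influence on these children exists with or without early notice, and the trial asks whether training helps despite it. This stands: the loss is possible, and its size is unknown.

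Four stronger readings are tempting, and the documents do not support them:

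- **That Aims 2 and 3 are diluted throughout.** Hypothesis 2.1 does not depend on transfer to the child, and RSA is already adjusted for its baseline.
- **That a null result would be uninterpretable.** With its confidence interval, it would still estimate the effect of training when the speech is known in advance.
- **That the child learns the whole task at session 1.** Item 14 mentions only a speech task with heart-rate monitoring. The topic and the video camera appear in item 12's session 2 steps, after training. The consent pages are not available, so the level of detail given there is unknown.
- **That the trial as run certainly has no safeguard.** Scripts and measures are attachments not seen here. The statement is limited to the visible text. Even so, no pre-training threat rating enters Analyses 2.1.

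It is also fair to say that a rating just before training could itself prompt the untrained appraisal and anchor the later one. Anchoring in both arms does not bias the comparison, but it could shrink the difference. That is a real, probably small, cost.

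**Conclusion.** The point holds as a matter of sensitivity and precision. The documents establish early disclosure to both mother and child, training up to two weeks later, a single post-discussion threat rating and unadjusted t-tests. They do not establish that home rehearsal occurs or how much it would matter. The randomised comparison remains valid. The exposure is a possible smaller effect and added between-dyad variance for hypotheses 2.2 and 3.1, of a size that cannot be derived.

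What can be quantified is the value of a pre-randomisation rating. At the assumed d = 0.5 and r = 0.5 to 0.7, power rises from 0.81 to 0.90–0.98 at alpha 0.05, and from 0.72 to 0.85–0.96 at 0.025. That gain is available whether or not rehearsal happens, and it shrinks if the correlation is lower. A rating not taken before training cannot be obtained afterwards, so the change is worth making for dyads not yet seen.

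**What to change.** 1. Keep the disclosure at consent. Add a line to the session 1 script asking dyads not to rehearse the speech before session 2, and record at session 2 whether they did.
2. At the start of session 2, before randomisation, have mother and child separately give a brief threat rating of the upcoming speech.
3. In Analyses 2.1, replace each t-test with an ANCOVA of the post-discussion rating on arm plus that person's own earlier rating. Leave Holm as it is.
4. If anchoring is a concern, omit the new rating and use as covariate the pre-training interpretation-bias score that mother and child already complete. It is not specific to the speech, so its correlation may be lower. At an assumed r = 0.3 and d = 0.5, the non-centrality is 2.850/0.954 = 2.988, giving power of 0.84 (alpha 0.05) or 0.76 (0.025).

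Cost: one script line, one question, about a minute per person and one covariate per model; no extra participants or staff. Limits: the request not to rehearse cannot be enforced, a first rating may anchor the second in both arms, and for Aim 3 only step 1 helps, because the covariate is proposed for Analyses 2.1 alone.

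### The t-tests for perceived threat (Analyses 2.1) and speech performance (H4.3) leave out an interpretation-bias score taken before randomisation; they are valid, and only precision is at issue

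*Combined protocol and SAP*

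**What the plan says.** Analyses 2.1 (H2 and H3) states that, with Holm's correction, "independent-samples t-tests will examine mean group differences (positive training vs. neutral training) in child and maternal ratings of perceived threat". For H4.3, the last part of Analyses 3.1 reads "we will conduct independent-samples t-tests to examine mean group differences in overall observer-rated performance during the speech". Neither names a covariate. Here, unadjusted means without covariates; the Holm correction in 2.1 is not in question.

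Item 12 gives the order of events at the second visit. First, "mothers and children will complete a computer task". Then: "Second, mothers will be randomly assigned to one of two groups". Item 14 identifies the task as an assessment of interpretation bias for mother and child, given twice: "one before the mother completes the interpretation bias training program, and one after".

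The repeat is described in two places. Item 12 says that after training "mothers will be asked to complete the first computer task again". Item 11 says that, after the mother-child discussion, children and mothers "will complete a second computerized assessment of interpretation biases to assess interpretation biases post-training". The two differ on who repeats the task and when, but both concern only the second administration.

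Elsewhere the plan does adjust for a baseline: H4.2 is an ANCOVA on baseline RSA.

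**The concern.** A score measured before randomisation and related to the outcome can remove part of the residual variance and so narrow the confidence interval for the treatment effect. The trial's own rationale (items 4 and 5) connects interpretation bias with perceived threat and child anxiety, so some correlation is plausible. The score is already collected for mother and child, yet these three comparisons do not use it.

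What is at stake is power and interval width at a fixed size of 65 per arm. Neither bias nor type I error is affected. The score is a related measure, not a baseline value of threat or of speech performance, so the gain may be small. Analyses 1.1, H4.1 and H4.2 are outside this point.

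**Working it through.** **Inputs from the documents.** 65 per arm (item 11), which agrees with the total of 130 dyads (item 4): 65 + 65 = 130. There is no power calculation to reproduce, because alpha, effect size, SD and power are not stated.

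**Assumptions.** Two-sided alpha 0.05, and 0.025 for the first Holm step of the two tests in 2.1. Standardised effect d from 0.3 to 0.6. Correlation r between covariate and outcome within arm from 0 to 0.5. No dropout.

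**Formulas (noncentral t).**
- t-test: df = 128, noncentrality = d / √(2/65).
- ANCOVA with one covariate: df = 127, noncentrality = d / √[(2/65)(1 − r²)(127/126)]. The factor 127/126 = 1.008 is the average cost of chance imbalance in the covariate.

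**Worked case, d = 0.5 and r = 0.3.**
- t-test: 0.5 / √0.03077 = 2.850, giving 80.8% power.
- ANCOVA: 0.03077 × 0.91 × 1.008 = 0.02822, and 0.5 / √0.02822 = 2.976, giving 84.0% power.

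**Results at d = 0.5.**

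| | Power, alpha 0.05 | Power, alpha 0.025 | Detectable d at 80% power, alpha 0.05 | Total N at which a t-test has the same power (alpha 0.05) |
|---|---|---|---|---|
| t-test | 80.8% | 71.9% | 0.495 | 130 |
| ANCOVA, r = 0 | 80.4% | 71.6% | 0.497 | 129 |
| r = 0.1 | 80.8% | 72.0% | 0.495 | 130 |
| r = 0.2 | 82.0% | 73.5% | 0.487 | 134 |
| r = 0.3 | 84.0% | 76.0% | 0.474 | 142 |
| r = 0.5 | 90.2% | 84.2% | 0.431 | 171 |

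**Other effect sizes, r = 0.3, alpha 0.05.** The gain is 2.9 points at d = 0.3 (from 39.7%), 3.7 at d = 0.4 (from 61.9%) and 1.9 at d = 0.6 (from 92.4%).

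**Break-even.** The variance is equal when (1 − r²)(127/126) = 1, so r² = 1/127 and r = 0.089. Counting the lost degree of freedom as well, it stays at 0.09 for every d from 0.3 to 0.6. The largest loss, at r = 0, is about 0.35 points at alpha 0.05 and about 0.4 at 0.025.

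**Both tests in 2.1 under Holm.** This was simulated with 20,000 trials per setting, d = 0.5 on both outcomes, an assumed residual correlation of 0.3 between them, and each outcome adjusted for its own covariate. The chance that both reject goes from 66.5% to 66.1% at r = 0, from 66.1% to 68.1% at r = 0.2, and from 66.9% to 71.6% at r = 0.3. Familywise type I error is about 4.9% with or without the covariate.

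**Why the first administration must be named.** The second score follows randomisation and may be changed by training. If training shifts it by 0.5 SD and its within-arm correlation with the outcome is 0.3, a true effect of 0.50 SD would be estimated as 0.50 − 0.3 × 0.5 = 0.35 SD. The current plan does not make this error; a loosely worded adjustment could.

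**The case against.** The strongest reply is that there is no error here. A two-sample t-test in a 1:1 randomised trial is a standard analysis, and choosing it is defensible. That stands, and it is why the point is minor.

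The second reply is that the benefit cannot be shown from the documents, because r is not given. At r = 0.2 and d = 0.5 the gain is 82.0 − 80.8 = 1.2 points, and below about 0.09 the change costs a little power. There is also a reason to expect a modest r. Item 6.03 requires every mother to score in the clinical range for anxiety and every child to have a primary anxiety diagnosis, and such range restriction can weaken correlations among anxiety-related measures. This limits the likely size of the gain. The range above starts at r = 0 for that reason.

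Third, H4.3 is the weaker case. Its outcome is scored by an observer and its covariate by the child's responses to a computer task, so both construct and source differ. H4.2 is not a close precedent, because there the covariate is the same measure as the outcome. This also stands.

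Fourth, other pre-randomisation measures exist, such as the session 1 questionnaires and the maternal anxiety score, and the task itself is described in an attachment that was not available here, so it may yield more than one score. This does not count against adjusting, but the plan would have to name the exact score.

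Against all this, the trade is lopsided: a loss of at most about 0.4 points if the score is uninformative, against gains of roughly 3 to 12 points at d = 0.5 if r lies between 0.3 and 0.5.

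**Conclusion.** The point holds as a minor matter of precision. Analyses 2.1 and H4.3 are valid as written, but they leave out a pre-randomisation score that is already collected. Assuming 65 per arm, two-sided 0.05 and d = 0.5, adjusting for it changes power from 80.8% by −0.4 points (80.4%) at r = 0, by nothing material at r = 0.1, and by +3.2 points at r = 0.3 and +9.4 at r = 0.5. The gain becomes clear only from about r = 0.3. Whether r reaches that level cannot be judged from the documents. It is more plausible for perceived threat than for observer-rated performance.

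**What to change.** Before outcomes are examined, amend Analyses 2.1 and the H4.3 part of Analyses 3.1 as follows:

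- Replace each t-test with an ANCOVA on treatment arm and one pre-specified covariate: the rated person's own interpretation-bias score from the first, pre-training administration. Use the mother's score for maternal threat, and the child's score for child threat and for speech performance.
- Name the exact score taken from the task.
- State that the post-training score is not used as a covariate.
- Keep Holm's correction across the two tests in 2.1.
- Report the planned t-tests as sensitivity analyses.

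No change to Analyses 1.1 or H4.1 is proposed. The cost is a change of wording, one of 128 degrees of freedom, and about 0.3 to 0.4 points of power if the covariate proves uninformative. No extra data, visits or participant burden are needed.
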